Acute Lung Injury (ALI) and the more severe variant ARDS are inflammatory conditions of the lung parenchyma^{1,2}. They cause impaired gas exchange and hypoxaemia with concomitant systemic inflammatory mediator release, frequently causing multiple organ failure and death^{1,2}. The Australian incidence of ARDS, from a survey of 21 ICUs in the late 1990's, was 28 cases per 100,000 per annum, with a 34% mortality rate³. More recently (2009), the ANZICS CTG Point Prevalence Investigators completed a point prevalence study demonstrating 42 out of 678 Australian ICU patients (6%) studied that day had ARDS. In a prospective, one month observational study of mechanically ventilated patients in 27 Australian ICUs in 2010, 27 out of the 650 patients studied (4%) developed ARDS. Of these 27, 6 (22%) had died and 10 (37%) remained hospitalised (5 (19%) in ICU) at day 28 (unpublished; NCT01093482). Finally, during the recent winter H1N1 2009 influenza pandemic, 49% of the patients admitted to Australian ICUs with influenza developed ARDS/pneumonitis⁴, 17% died in hospital and many required hypoxaemic rescue therapies⁵, such as extracorporeal membrane oxygenation (ECMO). Many of these patients were young (median age <60 years)⁴⁻⁷. These results are consistent with international experience^{8,9} that has shown that despite best supportive care, ARDS is common, and is associated with significant mortality and morbidity (prolonged mechanical ventilation and use of expensive hypoxaemic rescue therapies)^{7,8,10}. The hospital costs are also high with the average cost of each ARDS/pneumonitis patient with H1N1 influenza being AUD \$56,479, twice that of those without ARDS, and significantly higher for those requiring hypoxaemic rescue therapies (AU\$160,735 for ECMO)¹¹. Based on this, ARDS patients cost Australia at least \$20,000,000 in hospital expenses alone per annum. When these financial, mortality and morbidity costs are added to the significant functional and quality of life burden, which is still demonstrable one-year post-ARDS¹², the societal impact of ARDS is significant. Any intervention that impacts on mortality, time on mechanical ventilation and the need for expensive rescue therapies is likely to have important human, social and financial benefits.

ARDS pathophysiology and the effect of mechanical ventilation on organ failure

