 - Cause of death
- Safety outcomes:
 - Barotrauma
 - Severe hypotension
 - Serious adverse effects (SAEs)
- Economic outcomes:
 - Cost effectiveness analysis at 6 months (based on EQ-5D)

Determination of primary outcome

The primary outcome is the number of ventilator free days at day 28 post randomisation, and will be defined as the total number of days from day 1 to day 28 on which a patient is alive and receives no assistance from mechanical ventilation, if any period of ventilator liberation lasts at least 48 consecutive hours. Study day 1 is the day of enrolment and will continue until the end of the daily ICU chart used at that site, or the end of the calendar day if electronic data collection systems are used. If patients are on mechanical ventilation for any portion of the study day they will be classified as being on mechanical ventilation for that entire study day. To be considered truly liberated from mechanical ventilation, the patient will need to have at least 48 consecutive hours where they are liberated from mechanical ventilation. This means that if, for example, they have 47 consecutive hours liberated from mechanical ventilation and then receive mechanical ventilation, none of this time will be considered as ventilator free. But if, for example, they have 49 consecutive hours liberated from mechanical ventilation and then receive mechanical ventilation, all of this time will be considered as ventilator-free, to contribute to classification of the ventilator-free status for each study day. Non-invasive mechanical ventilation will not be considered assistance if it is provided by face or nasal mask, but will be considered assistance if it is provided by tracheostomy. Any patient who dies before weaning from mechanical ventilation will be allocated the value of 0 ventilator free days. Any patient who dies after weaning from mechanical ventilation (ie. they have at least 48 consecutive hours off mechanical ventilation) but before day 28 will not have the days after their death until day 28 considered as a ventilator free day.

STUDY METHODOLOGY

Study outline

A phase II, multi-centre, prospective, randomised controlled trial.

Study population

Patients meeting all the inclusion and none of the exclusion criteria in the ICU will be eligible for enrolment.

Inclusion criteria

Adult ICU patients who meet all of the following criteria:

- Currently intubated and receiving mechanical ventilation

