Independent senior statisticians at Monash University will perform data analysis. Baseline and outcome variables will be compared using Chi-square tests for categorical variables, Student's t-test for normally distributed continuous variables and Wilcoxon rank-sum tests for non-normally distributed continuous variables. Duration of ventilation will be analysed using Cox-Proportional Hazards regression with deceased patients censored at death, allowing for results to be reported using Kaplan Meier curves. Furthermore, duration of ventilation will be stratified into survivors and non-survivors. If as expected, the duration of ventilation in each strata is well approximated by a log-normal distribution, this will enable log-transformed duration of ventilation to be analysed using parametric analysis (student t-tests) and reported as a ratio (95%CI). If normality cannot be achieved then the data would subsequently be analysed non-parametrically. Should any baseline imbalances be found to exist between groups, additional sensitivity analysis will be performed using Cox Proportional Hazards regression adjusting for imbalanced covariates. All analyses will be intention-to-treat. A complete statistical analysis plan will be finalised prior to study completion.

Interim analysis

One midpoint interim analysis (after primary outcome data is available for 170 patients) will be performed to assess accumulated safety data. This will be reported to the Data Safety Monitoring Committee, but will not be made available to the Management Committee or to study sites.

Subgroup analyses

We plan to compare study outcomes in the following pre-specified subgroups:

- (a) Patients with severe ARDS ($\text{PaO}_2/\text{FiO}_2 < 100$) versus patients with moderate ARDS ($\text{PaO}_2/\text{FiO}_2$ 100-200 mmHg) at enrolment.
- (b) Patients with diffuse ARDS versus patients with focal ARDS at enrolment (determined by independent radiologists).
- (c) Patients who are responders to the open lung strategy versus patients who are non-responders (defined as meeting lack of improvement in static lung compliance definition).

SAFETY OF SUBJECTS

Data Safety Monitoring Committee

An independent Data Safety Monitoring Committee, comprising experts in clinical trials, biostatistics and intensive care will be established. The committee will be responsible for monitoring mortality related to serious adverse events, serious adverse events and reviewing the interim safety analysis.

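### Kaplan-Meier curves of ventilation duration with deaths censored overstate the proportion liberated alive, and the tests within survivors and non-survivors are not randomised comparisons (supporting analysis, minor)

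*Combined protocol and SAP*

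**What the plan says.** The section Statistical and analytical plan gives duration of ventilation its own methods. The first is Cox regression "with deceased patients censored at death, allowing for results to be reported using Kaplan Meier curves". The second is a split by vital status: "Furthermore, duration of ventilation will be stratified into survivors and non-survivors". If log duration looks normal in each stratum, it is compared by t-test and the result is given as a ratio with a 95% confidence interval; if not, a non-parametric analysis is used. The text does not say that the ratio is between arms, but no other reading makes sense. The same section adds: "A complete statistical analysis plan will be finalised prior to study completion". No competing-risk method or cumulative incidence curve appears anywhere in the document.

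Duration of ventilation is listed under Data variables collected. It is not among the primary or secondary outcomes under Study outcome measures. The primary outcome, ventilator-free days (VFDs), deals with death directly: "Any patient who dies before weaning from mechanical ventilation will be allocated the value of 0 ventilator free days". Mortality is a separate secondary outcome.

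**The concern.** A patient who dies on the ventilator can never be liberated. Censoring that death treats the patient as someone who would have gone on to be liberated at the same rate as those still ventilated. One minus the Kaplan-Meier curve then describes liberation in a hypothetical setting without death. A reader will take it as the share of patients who came off the ventilator alive, and for that it is too high.

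The second analysis conditions on something that happens after randomisation. If the ventilation strategy changes who survives, the survivors in the two arms are no longer comparable groups, and a ratio with a confidence interval can show a difference in duration where weaning is unaffected. The intention-to-treat statement does not repair this, because the restriction is on the outcome and not on compliance.

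**Working it through.** The documents give no figure for the duration analysis, so there is nothing of the plan's own to reproduce.

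**Kaplan-Meier display**

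Inputs, from the Background section on acute respiratory distress syndrome:

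- A local one-month study of 27 patients: "6 (22%) had died and 10 (37%) remained hospitalised (5 (19%) in ICU) at day 28".
- An older Australian survey: "28 cases per 100,000 per annum, with a 34% mortality rate", with no time point given.

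Assumptions: both mortality figures are taken as day-28 deaths; ICU stay stands in for ventilation, so S = 0.19 (5 of 27, hence imprecise); hazards are constant.

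Let S be the proportion still ventilated at day 28 and D the proportion dead on the ventilator by then.

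- Total hazard: h = −ln(S)/28 = −ln(0.19)/28 = 0.0593 per day
- Death hazard: ld = h × D/(1 − S)
- Liberation hazard: le = h − ld
- True proportion liberated alive: 1 − S − D
- Kaplan-Meier reading: 1 − exp(−28 × le)

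For D = 0.22: ld = 0.0593 × 0.22/0.81 = 0.0161, le = 0.0432, reading = 1 − exp(−1.210) = 70.2%, against a true 59.0%.

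| D, with S = 0.19 | le | True | Kaplan-Meier reading | Excess (points) |
|---|---|---|---|---|
| 0.22 | 0.0432 | 59.0% | 70.2% | 11.2 |
| 0.34 | 0.0344 | 47.0% | 61.8% | 14.8 |
| 0.11 (half of 0.22) | 0.0513 | 70.0% | 76.2% | 6.2 |
| 0.17 (half of 0.34) | 0.0469 | 64.0% | 73.1% | 9.1 |

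The halved rows matter because the protocol provides for later deaths: "Any patient who dies after weaning from mechanical ventilation" keeps the ventilator-free days before death.

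Sensitivity:

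- With all deaths on the ventilator, the excess at 22% and 34% deaths is 14 and 20 points if S = 0.10, and about 10 and 12 points if S = 0.25.
- With log-normal liberation times (log-SD 0.78) and S = 0.19, it is 7 to 13 points at 22% and 10 to 18 points at 34%, the lower ends having half the deaths on the ventilator.
- Timing sets the bounds. If every death on the ventilator followed the last liberation, the excess would be nil. If every such death came first, the reading would be (1 − S − D)/(1 − D): 0.59/0.78 = 75.6% and 0.47/0.66 = 71.2%, an excess of 17 and 24 points. It is never negative.

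**Survivor comparison**

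This needs simulation, and every input below is an assumption:

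- 170 patients per arm, followed to day 28.
- Log duration has SD 0.78 and the same distribution in both arms, so there is no weaning effect.
- The death hazard rises with a severity score whose correlation with log duration is 0, 0.3 or 0.77.
- Deaths on the ventilator are 24% in one arm and 34% in the other. All other patients count as survivors.
- 19% of the lower-mortality arm is still ventilated at day 28.
- The excess deaths occur either at a constant rate or only after day 7.

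Results, as higher- over lower-mortality arm:

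- Survivor ratio: about 0.93 to 0.97.
- Nominal 5% t-test on log duration in survivors: rejects in about 8 to 16% of trials. A rank test gives about 8 to 18%. The ends of these ranges move by about a point between runs.
- Equal mortality (24% in both arms): ratio about 1.00, rejection about 5%.

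A differently built model (162 per arm, 34% v 24%) gave a lower- over higher-mortality ratio of 1.05, which is 1/1.05 = 0.95 in the direction used here, with 7.5% rejection.

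**Non-survivor comparison**

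For deaths on the ventilator, duration is time to death. In the same simulation the ratio is about 0.89 to 0.90 when the excess deaths run at a constant rate from the start, and about 1.17 to 1.23 when they fall after day 7. The direction depends on timing that the documents do not give.

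**The case against.** Several counter-arguments carry weight.

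- *The Cox model with deaths censored is legitimate.* This stands. A reader might infer that censoring deaths invalidates the whole analysis. It does not: the hazard ratio is a cause-specific one for liberation. Only the curve, read as a proportion, is at fault.
- *The plan does not say the curve will be read as an absolute proportion.* True, but that is how such a curve is normally read. The overstatement concerns liberation alive. In the 22% example, 59% + 22% = 81% are off the ventilator if deaths are counted, which is above the 70% reading.
- *The mortality difference is invented.* It is assumed. The documents give none and leave the question of mortality to a later phase III trial. With equal mortality the survivor test is sound. Mortality is also reported separately, so readers would see a gap. The Kaplan-Meier point needs no difference.
- *The t-test may never be used.* Truncating follow-up at day 28, which the plan does not specify, piles up values there, and normality would probably fail. The planned fallback is non-parametric. That alters the figures slightly but leaves the selection in place.
- *The SAP will settle it.* It can, but the protocol already names these methods, and without a correction they carry forward.

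**Conclusion.** The point holds and is minor. The direction of the Kaplan-Meier error is certain wherever deaths on the ventilator precede some liberations. Its size, about 11 to 15 points or 6 to 9 if half the deaths occur off the ventilator, rests on constant hazards, ICU stay as a proxy for ventilation, and background mortality read as day-28 deaths. The survivor comparison is non-randomised as a matter of principle. Its distortion (ratio about 0.93 to 0.97, rejection about 8 to 16%) depends on an assumed mortality difference.

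Two stronger readings are not supported. One is that both strata would favour the higher-mortality arm and produce false positives. Among non-survivors no general direction can be stated, and a shorter time to death on the ventilator is a real difference, not a spurious one. The other is that the trial's main result is compromised. Duration is not a listed outcome, and the VFD outcome scores death before weaning as 0.

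**What to change.** In the SAP still to be finalised:

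- Replace the Kaplan-Meier curves with cumulative incidence curves, by arm, of liberation alive (using the 48-hour rule under Determination of primary outcome) and of death on the ventilator. Keep the Cox model and label its result a cause-specific hazard ratio for liberation.
- Label the durations in survivors and non-survivors as descriptive, non-randomised summaries that carry no efficacy claim, and state the time point at which survival is judged.

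This costs wording and slightly more analysis work in standard software, with no new data or patients. The stratum ratios lose their inferential status.

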There is substantial experimental evidence, biological rationale, and supportive clinical evidence to suggest the efficacy of the PHARLAP ventilation strategy in ARDS. However, mostly because of concern that SRM's and high PEEP may cause barotrauma and haemodynamic instability in critically ill patients, previous trials may have been sub-optimally designed to determine the true efficacy of such an OLS. The PHARLAP strategy is more intensive, more individual patient tailored and at least as safe as previously studied open lung strategies. In addition, the PHARLAP strategy can be delivered by almost any clinician using any conventional mechanical ventilator and if proven effective and safe, would be highly applicable for widespread use (including the developing world). Given the significance and cost of ARDS, the possible benefits of this strategy, the growing number of recommendations for the use of a LRM with elevated levels of PEEP^{18,19,46}, this study is an important undertaking. The trial will determine whether the PHARLAP ventilation strategy is effective in increasing ventilator free days in patients with ARDS. If the PHARLAP strategy is proven to improve ventilator free days it will provide a strong impetus to conduct an international phase III RCT to determine the effects of this strategy on mortality.

OBJECTIVES

Aim

To determine the efficacy of the PHARLAP strategy compared to a control ventilation strategy in increasing ventilator free days assessed during the 28 days post randomisation.

Hypothesis

The PHARLAP strategy group will have a higher number of ventilator free days at day 28 than the control group.

STUDY OUTCOME MEASURES

Primary outcome

- Number of ventilator free days at day 28 post randomisation

Secondary outcome

- Physiological outcomes:
 - PaO₂/FiO₂ ratio
 - Static lung compliance
- Inflammatory outcomes:
 - Baseline to day 3 change in IL-8 and IL-6 concentrations in broncho-alveolar lavage fluid
 - Baseline to day 3 change in IL-8 and IL-6 concentrations in plasma
- Clinical/patient-centred efficacy outcomes:
 - Use of rescue therapies for severe hypoxaemia – inhaled nitric oxide, inhaled prostacyclin, prone positioning, high frequency oscillatory ventilation and extracorporeal membrane oxygenation (ECMO)
 - Incidence of acute kidney injury (AKI)
 - ICU and hospital length of stay
 - Quality of life assessment (SF-36v2 and EQ-5D) at 6 months
 - Mortality at ICU/hospital discharge, 28 days, 90 days and 6 months

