Pressure Support Ventilation (PSV) mode should be used to transition the patient from controlled to spontaneous mechanical ventilation. This mode should also be used if there are significant problems using controlled ventilation with patient-ventilator dysynchrony, difficulty in meeting aims, or because of strong clinician preference. The patients should be in either (1) SIMV Volume/Pressure Control mode with PSV or (2) PSV alone.

In PSV the goals of mechanical ventilation remain as follows:

- Tidal volume: ≤ 6 ml/kg PBW
- Plateau pressure [for controlled breaths]: ≤ 30 cmH₂O
- Total pressure [for spontaneous breaths] (ie. set inspiratory pressure + PEEP): ≤ 30 cmH₂O
- Breath rate: ≤ 35 breaths/minute
- pH: 7.30-7.45 (do not aim for a specific PaCO₂)
- SaO₂: 90-95% (if a PaO₂ is available, the aim for this is 60-80 mmHg).

Tidal volume targets should only be relaxed when the patient is clinically stable and receiving FiO₂ ≤ 0.5 and PEEP ≤ 10 cmH₂O. The inspiratory pressure for PSV can be adjusted down to a minimum of 5 cmH₂O (if tidal volume > 6 ml/kg PBW). If the tidal volume remains > 8 ml/kg PBW, there should be strong consideration to increase sedative drugs or to use a neuromuscular blocking drug so that controlled ventilation can replace (partially or completely) spontaneous mechanical ventilation. **Whilst PSV mode is being used, tidal volumes should be carefully monitored (including the use of mechanical ventilator alarms) with the aim that these remain approximately 6 ml/kg PBW.**

Management of severe hypoxaemia in the control group

If control group patients have a PaO₂ < 60 mmHg or a SaO₂ $< 90\%$ whilst receiving an FiO₂ and PEEP combination in any of the 5 columns at the right end of the FiO₂ and PEEP combination table (ie. FiO₂ ≥ 0.8 and PEEP ≥ 14), hypoxaemic rescue therapies should then be considered. These include prone positioning, inhaled nitric oxide, inhaled prostacyclin, high frequency oscillation and extracorporeal membrane oxygenation (ECMO), depending on the practice, availability, feasibility in the specific site and appropriateness.

No recruitment manoeuvres should be performed in control group patients unless there is no other feasible hypoxaemic rescue therapy able to be performed. Staircase recruitment manoeuvres should never be performed in the control group.

Resumption of the control group mechanical ventilation strategy should occur as soon as possible.

Weaning of mechanical ventilation in the control group

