If haemodynamic instability occurs during the combined open lung procedure (mainly during the SRM), vasopressors should be considered initially. Intravenous fluid boluses should be administered if vasopressor requirements increase rapidly.

Use of corticosteroids in both groups

Steroids should not be used specifically for ARDS after day 7⁵¹.

Other interventions in both groups

All other interventions will not be standardised. Given the possibility of confounding by different utilisation rates of various interventions between groups, data will be collected on haemodynamics (daily central venous pressure, blood pressure and heart rate), fluid balance, pulmonary artery catheter usage, intravenous bicarbonate usage, renal replacement therapy usage, neuromuscular blocking drug usage, corticosteroid usage and hypoxaemic rescue therapy usage.

Discontinuation of treatment

Patients in both groups will receive their assigned ventilator strategy until any of the following occur:

1. The patient is no longer receiving mechanical ventilation
2. The patient dies or is discharged from the Intensive Care Unit
3. The patient or surrogate decision-maker withdraws informed consent.

Table of events

Please see Appendix 3

Laboratory sampling

Blood (10 ml centrifuged to isolate plasma) and BAL (10 ml taken using the technique described above) samples will be collected and stored -80°C at each site at baseline and day 3. Samples will be shipped in 2 batches to a central processing laboratory (Flinders Medical Centre) for quantification of IL-6, IL-8 and protein concentration by blinded laboratory scientists.

ETHICAL CONSIDERATIONS

Guiding principles

This study is to be performed in accordance with the ethical principles of the Declaration of Helsinki (June 1964 and amended 1975, 1983, 1989, 1996, 2000, 2008 and Note of Clarification 2002 and 2004), ICH GCP Notes for Guidance on Good Clinical Practice (CPMP/ICH/135/95) annotated with Therapeutic Goods Administration comments, NHMRC National Statement on Ethical Conduct in Research Involving Humans (March 2007); the New Zealand Interim Good Clinical Research Practice Guidelines (Volume 2 1998 and Volume 3 2000) and ICH GCP Notes for Guidance on Good Clinical Practice (CPMP/ICH/135/95).

Ethical issues of the study

The two major ethical considerations in this study are:

- The enrolment of participants who are unable to provide their own informed consent

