Adverse events

Adverse events are defined as any untoward medical occurrence in a patient or clinical investigation subject administered an investigational intervention and does not necessarily have to have a causal relationship with this intervention (adapted from the Note for Guidance on Clinical Safety Data Management: Definitions and Standards for Expedited Reporting (CPMP/ICH/377/95 July 2000).

It is recognised that the patient population with critical illness and ARDS will experience a number of common aberrations in laboratory values, signs and symptoms due to the severity of the underlying illness and the impact of standard therapies. These will not necessarily constitute an adverse event unless they require significant intervention or are considered to be of concern in the investigator's clinical judgement.

In all cases, the condition or disease underlying the symptom, sign or laboratory value should be reported e.g. renal failure rather than hyperkalaemia, and agitation rather than self-extubation.

Serious adverse events

Serious Adverse Events (SAE) are defined in accordance with the Note for Guidance on Clinical Safety Data Management: Definitions and Standards for Expedited Reporting (CPMP/ICH/377/95) (July 2000) as any one of the following untoward medical occurrences:

- Results in death
- Is life-threatening
- Requires inpatient hospitalisation or prolongation of existing hospitalisation
- Results in persistent or significant disability/incapacity
- Is a congenital anomaly/birth defect
- Is an important medical event which may require intervention to prevent one of the previously listed outcomes

In this study all SAEs will be reported if they possibly, probably or causally are related to study enrolment. However, consistent with the advice of Cook et al, adverse events already defined and reported as study outcomes (mortality) will not be labelled and reported a second time as serious adverse events.

Reporting of SAEs

Separate case report forms will be developed to record adverse events and serious adverse events.

SAEs which occur from the time of enrolment until day 90 follow-up will be reported to the coordinating centre via the internet-based SAE form. SAEs should be reported to the coordinating centre within 24 hours of study staff becoming aware of the event.

Minimum information to report will include:

- Patient initials and study number
- Nature of the event
- Commencement and cessation of the event

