- An investigator's opinion of the relationship between study involvement and the event (unrelated, possibly, probably or definitely related).
- Whether treatment was required for the event and what treatment was administered.

Website address: <https://pharlap.org.au>

Telephone Numbers:

ANZIC-RC: [name]

ANZIC-RC: [name]

Chief investigator: [name]

SAEs must be reported using the study website. The event and report may be discussed with the coordinating centre staff or chief investigator if necessary. Coordinating centre staff will be responsible for following-up SAEs to ensure all details are available. The site principal investigator is responsible for inform the relevant HREC of all SAEs which occur at their site, in accordance with local requirements.

FUNDING

The PHARLAP study is funded by project grants from the National Health and Medical Research Council (NHMRC) (Project grant no APP1021203), the Alfred Hospital, and the Health Research Council of New Zealand. The ANZIC-RC will supply infrastructure and administrative support.

PUBLICATION

The study will be conducted in the name of the PHARLAP investigators, the ANZIC-RC and the Australian and New Zealand Intensive Care Society Clinical Trials Group (ANZICS CTG). The study has been endorsed by the ANZICS CTG. The principal publication from the study will be authored as "The PHARLAP Study Investigators for the ANZICS CTG". This will be on behalf of the writing committee and all PHARLAP Investigators with full credit being assigned to all collaborating investigators, research coordinators and institutions. Where an individual's name is required for publication it will be that of the writing committee, with the chair of the writing committee listed first and subsequent authors listed alphabetically.

Funding bodies will be acknowledged in the publication.

Other manuscripts and sub-studies may be authored differently but these must follow the conditions of ANZICS CTG endorsement and be approved by the PHARLAP MC. This may lead to manuscripts authored by a list of individual authors on behalf of the PHARLAP Study Investigators for the ANZICS CTG.

PROJECT TIMELINE

Timeframe Indicator	Milestone
January 2011	ANZICS CTG endorsement
April 2011	NHMRC funding application submitted
August 2011	Alfred Hospital funding application successful
October 2011	NHMRC funding application successful
November 2011	Commencement of study organisation

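### Serious adverse events are a safety outcome, but one reporting rule admits them on the investigator's view of relatedness in visibly different arms, and other passages contradict that rule

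*Combined protocol and SAP*

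**What the plan says.** The secondary outcomes (Study Outcome Measures) include, under safety, barotrauma, severe hypotension and "Serious adverse effects (SAEs". The Statistical and analytical plan compares categorical outcome variables with Chi-square tests and defers a complete plan to a later document. The Data Safety Monitoring Committee section gives that committee the task of monitoring SAEs.

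On what is reported, the text points two ways:

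- Serious adverse events: "In this study all SAEs will be reported if they possibly, probably or causally are related to study enrolment". The same paragraph excludes events already captured as study outcomes, naming mortality.
- Reporting of SAEs, window: "SAEs which occur from the time of enrolment until day 90 follow-up will be reported to the coordinating centre via the internet-based SAE form". No relatedness condition is attached.
- Reporting of SAEs, minimum information: "An investigator's opinion of the relationship between study involvement and the event (unrelated, possibly, probably or definitely related". An unrelated category is therefore provided on the report.

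The adverse event definition says that an event "does not necessarily have to have a causal relationship with this intervention". The next paragraph, however, leaves common aberrations of critical illness out unless they need significant intervention or concern the investigator. Appendix 3 schedules adverse events to ICU discharge and SAEs to hospital discharge.

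The only blinding described for an assessor is in Laboratory sampling: "quantification of IL-6, IL-8 and protein concentration by blinded laboratory scientists".

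**The concern.** A between-arm count is interpretable when an event has the same chance of being counted in either arm. Under the relatedness rule, an SAE counts after a causal judgement by someone who can see the assignment. The arms cannot be confused: "Staircase recruitment manoeuvres should never be performed in the control group", whereas PHARLAP patients have a staircase manoeuvre daily for up to five days, with PEEP stepped towards 40 cmH2O. The Significance section also records a "concern that SRM's and high PEEP may cause barotrauma and haemodynamic instability in critically ill patients", which gives clinicians an arm-specific reason to consider a link. The control strategy is based on the ARDSnet protocol, so it is less clear what relatedness to enrolment would mean there.

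At stake are one listed safety outcome and one of the monitoring committee's inputs, in a phase II trial intended to inform a larger one. Because the reporting sentences conflict, sites may also apply different filters, and the pooled count would then have no single definition.

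**Working it through.** **Inputs from the documents.** Enrolment is 340. The allocation ratio is not stated; 1:1 is assumed, giving 340/2 = 170 per arm. The interim safety look is after 170 patients, or 85 per arm. The test is Chi-square, taken as two-sided at 0.05. The sample-size chain supplies only N and reproduces closely: 282 × 1.15 = 324, and 324/0.95 = 341 against 340 planned.

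**Inputs assumed.** The documents give no SAE risk and no probability that an SAE is judged related. Both are varied below.

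**Model.** Let t be the true SAE risk, equal in both arms, and q1 and q2 the probabilities that an SAE is judged related in PHARLAP and control. The reported risks are t × q1 and t × q2, so the expected reported risk ratio is (t × q1)/(t × q2) = q1/q2, whatever t is. This step needs no assumed rate.

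**False-positive rate.** Exact rejection probability of the uncorrected Chi-square test, with no true difference and t = 20%:

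| q1 v q2 | Reported risks | Ratio | 170 per arm | 85 per arm |
|---|---|---|---|---|
| 30% v 30% | 6% v 6% | 1.0 | 5% | 4% |
| 30% v 20% | 6% v 4% | 1.5 | 13% | 8% |
| 40% v 20% | 8% v 4% | 2.0 | 34% | 17% |

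For 40% v 20% at 170 per arm, t = 10% gives 18%, t = 30% gives 50% and t = 40% gives 63%. If every SAE is counted and ascertainment is equal, the rate stays at 5.0% to 5.2% for t from 10% to 40%.

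**Masking.** Suppose true risks of 30% (PHARLAP) v 15% (control). Counting every SAE detects the difference in 92% of trials at 170 per arm. With attribution of 20% v 40%, the reported risks are 0.30 × 0.20 = 6% and 0.15 × 0.40 = 6%, and the test rejects in about 5%. Even an equal 30% filter (reported 9% v 4.5%) cuts detection to 38%, because fewer events are counted.

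**Passages side by side.** The definition section makes relatedness a condition. The day-90 sentence has no condition, and the minimum-information list includes an unrelated category. A site could follow either in good faith. The window also differs: day 90 in the text, hospital discharge in Appendix 3.

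**The case against.** The strongest reply is that the rule does not contain the word only. The day-90 sentence and the unrelated category suggest that unrelated SAEs also reach the database, in which case an all-SAE comparison is already possible. This stands in part. A reader might infer that unrelated SAEs are certainly discarded, and the documents do not establish that. They do leave two reporting rules in force, and the explicit one conditions on relatedness.

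Second, much of the safety comparison lies outside the filter. Mortality, barotrauma and severe hypotension are separate outcomes with no attribution condition, and the last two are close to the harms the protocol itself names. This stands. A reader might infer that the whole safety assessment is compromised, but the text does not support that. What remains is other non-fatal SAEs, such as a survived cardiac arrest or an arrhythmia.

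Third, the adverse event form might be taken as an unfiltered source because it needs no causal link. It is not: investigator judgement decides whether common aberrations count as adverse events. Using that form removes the causality filter and leaves this discretion in place.

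Fourth, all rates are assumed. A gap of 50% v 10% at a true risk of 20% would give about 91% false significance, but nothing in the documents supports a fivefold gap. Nor do they settle the direction: over-attribution to the new strategy is plausible, and so is under-attribution by clinicians who favour it. That the investigators are unblinded is itself inferred from the design, although the procedures leave little doubt. The Chi-square test of SAEs is inferred from a general sentence, and the full analysis plan is still to come.

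**Conclusion.** The point holds in a limited form. The sentences on SAE reporting contradict one another. If the relatedness rule is the one followed, the by-arm SAE count mixes harm with arm-dependent attribution. The structural result, a reported risk ratio of q1/q2 when true risks are equal, rests only on attribution not depending on the true risk.

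The size depends on assumed inputs: about 13% to 34% false significance for attribution gaps of 30% v 20% to 40% v 20% (170 per arm, true risk 20%), against about 5% with no gap. The distortion needs attribution to differ by arm, and it can create a signal or hide one. It concerns non-fatal SAEs other than barotrauma and severe hypotension, and it does not touch the primary outcome. The change should be made because it is cheap and a named safety outcome depends on it.

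**What to change.** - Add a seriousness field to the existing adverse event form. Base the by-arm SAE comparison and the monitoring committee's tables on all events meeting a seriousness criterion, regardless of judged relatedness, over the adverse event window in Appendix 3 (day 1 to ICU discharge).
- Continue to report SAEs after ICU discharge over the existing SAE window, and show them by arm, so that later events are not lost.
- Record relatedness as an attribute. Use it only to decide 24-hour expedited reporting, and present investigator-attributed SAEs by arm descriptively, without a test.
- Keep mortality as its own outcome.
- Reconcile the Serious adverse events paragraph with Reporting of SAEs on whether unrelated SAEs are submitted, and the day-90 window with the hospital-discharge window in Appendix 3.

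The cost is wording in the protocol and the analysis plan still to be finalised, one form field, somewhat more recording and coding, and higher event counts in both arms. Investigator discretion over what counts as an adverse event remains, so the bias is reduced and not eliminated.
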